## **8.11. Methods**

### **8.11.1. Medication**

The hospital's standard protocol should be followed with respect to medication pre-procedure and during the procedure.

### **8.11.2. Pre-procedure**

#### Zenith® Branch Endovascular Graft-Iliac Bifurcation Sizing

The Zenith® Branch Endovascular Graft-Iliac Bifurcation is sized based on the findings from pre-operative radiographic studies, including computerized tomography (CT) and

conventional angiography. Zenith® Branch Endovascular Graft-Iliac Bifurcation component selection should be based on the recommended sizing guidelines in the Instructions for Use of this device.

#### Atrium iCAST™ Sizing

The Atrium iCAST™ stent is sized based on the findings from pre-operative radiographic studies, including computerized tomography (CT) and conventional angiography, if needed. Final sizing is based on findings from intra-operative angiography.

#### Additional Component Sizing

Since the patient will undergo concomitant AAA endovascular repair with a standard Zenith Flex® AAA Endovascular Graft (main body and iliac legs), all proximal aortic measurements should be assessed and sized according to Zenith Flex® AAA Endovascular Graft Instructions for Use (IFU).

#### **8.11.3. Procedure**

Standard techniques for placement of arterial access sheaths, guiding catheters, angiographic catheters, and wire guides should be employed during use of the Zenith® Branch Endovascular Graft-Iliac Bifurcation, Atrium iCAST™, and Zenith Flex® AAA Endovascular Graft and iliac legs. All components are compatible with 0.035 inch diameter wire guides.

Refer to institutional protocols relating to anesthesia, anticoagulation and monitoring of vital signs. Position the patient on an imaging table allowing fluoroscopic visualization from the aortic arch to the femoral bifurcations. Expose both common femoral arteries using standard surgical technique and establish adequate proximal and distal vascular control of both femoral vessels.

Refer to the Instructions for Use for complete details regarding use of the Zenith® Branch Endovascular Graft-Iliac Bifurcation, the Zenith Flex® AAA Endovascular Graft, and iliac legs. A commercially available balloon-expandable covered stent (Atrium iCAST™ stent) will be placed to preserve blood flow to the internal iliac artery; likewise, the Manufacturers' Instructions for Use should be referred to for additional information. Fluoroscopic guidance and angiography should be used throughout the procedure to verify positioning of the device with respect to the patient's anatomy.

#### **8.11.4. Post-operative Treatment of Endoleaks**

The presence of contrast media in the aneurysm sac is indicative of an endoleak. Type I or type III endoleaks may warrant treatment at the time of implantation. To classify an endoleak as type II, imaging documentation must clearly show the source. Due to the anatomy of the iliac bifurcation area, the presence of a type II endoleak is unlikely; however, should one occur, the patient should be treated at the physician's discretion. Type IV endoleaks are generally associated with grafts with a high porosity and are unlikely with this graft.

#### **8.12. Period of Use for the Device or its Control**

The follow-up period for the clinical investigation should permit the demonstration of performance over a period of time sufficient to represent a realistic test of the performance of the device and allow identification and risk assessment of any associated adverse device effects over that period.

#### **8.13. Safety Monitoring**

A Data Safety Monitoring Board (DSMB), consisting of independent physicians who are not investigators in the extended study and do not have a perceived conflict of interest with the conduct and administration of the extended study, will be convened on a regular basis to evaluate the extended study progress and review adverse events.

An independent Clinical Events Committee (CEC) will be established. Any adjudication of clinical events will be performed according to standard operating procedures to assess whether the events were due to a pre-existing condition, procedure-related, technique-related, and/or device-related. In addition, a core laboratory will be established to independently review available imaging.

Regularly scheduled monitoring, including on-site visits, will be conducted, in part, for identification of adverse events and assurance that they are correctly reported to the DSMB and CEC.

### **9.0. Emergency Situations**

Patients will not be treated with the Zenith® Branch Endovascular Graft-Iliac Bifurcation in emergency situations where prior consent of the patient (or legally authorized representative) is not possible. Since the Zenith Flex® AAA Endovascular Graft is

approved for commercial use, the physician may use the Zenith Flex® AAA Endovascular Graft to treat a patient in an emergency situation; however, that patient would not be enrolled in the current study and no data would be collected under this investigational plan. The Zenith® Branch Endovascular Graft-Iliac Bifurcation and Atrium iCAST™ may not be used to treat a patient in an emergency situation.

## **10.0. Deviations from the Clinical Investigation**

Deviations or non-compliances will be recorded together with an explanation. Deviations shall be reported to the Sponsor, regulatory authorities, and local IRB/ethics committee as required.

When available, the reasons for withdrawal and discontinuation of any patient from the investigation shall be recorded. If such discontinuation is because of problems with safety or lack of effectiveness, that patient shall still be followed-up in the investigation, if possible.

If appropriate, corrective and preventive actions will be discussed by the sponsor, investigator, and/or IRB to determine a suitable course of action.

## **11.0. Amendments to the Clinical Investigation**

If necessary, changes to the clinical investigation plan, which affect the validity of the data; relationship of likely patient risk to benefit; scientific soundness; or rights, safety, or welfare of human subjects, will be approved by the regulatory authority and local institutional review board/ethics committee prior to implementation.

## **12.0. Informed Consent**

A written informed consent must be obtained from all study patients (or their legally authorized representative), in accordance with applicable regulatory requirements, prior to enrollment in the trial. If new information is obtained after a patient receives treatment with the device, any patient who has not exited the study will be informed about the new information, and will be reconsented at the discretion of the investigator and/or the site's IRB.

### **13.0. Procedure for Reporting Adverse Events and Adverse Device Effects**

Events known to be related to pre-existing conditions or existing at enrollment are not considered adverse events (e.g., new treatment for congestive heart failure diagnosed prior to the procedure). Additionally, common standard of care practices are not considered adverse events (e.g., supplemental oxygen provided for all patients discharged from institutions at high altitudes).

Adverse events are reported using the appropriate case report form (Adverse and Other Event form). Each completed form is to be submitted to the data coordinating center, who will inform the Sponsor accordingly. In cases of adverse device effects (typically reported on appropriate imaging form rather than Event form) or serious adverse events, completed forms should be submitted to the data coordinating center immediately after the site learns of the event.

The data coordinating center will notify the Sponsor accordingly. In accordance with applicable requirements, the investigator will notify the local institutional review board/ethics committee, while the Sponsor will notify the regulatory authority. The DSMB and CEC will also review applicable adverse events.

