### **3.0. Clinical Investigation Plan Overview**

The purpose of this extended study is to evaluate the safety and effectiveness of the Zenith® Branch Endovascular Graft-Iliac Bifurcation in combination with the commercially available Atrium iCAST™ covered stent in patients with an unsuitable distal sealing site for a Zenith® iliac leg component proximal to the common iliac bifurcation to maintain internal iliac artery patency during endovascular aneurysm repair.

This extended study is designed as a prospective, non-randomized study enrolling up to 60 additional patients to receive the Zenith® Branch Endovascular Graft-Iliac Bifurcation at up to 30 clinical sites. This additional enrollment will include a cohort of 40 patients who will be treated with the Zenith® Branch Endovascular Graft-Iliac Bifurcation in combination with the Atrium iCAST™ covered stent, which is replacing the alternate covered stents used in a portion of the additional patients already enrolled in the extended study (18 patients) as well as the initial cohort of 40 patients accrued prior to the extended study. Patients with anatomy amenable to endovascular repair, who meet other enrollment criteria (see section 8.6), will be included in this extended study, which will be complete with respect to enrollment upon accrual of 40 patients treated with the Zenith® Branch Endovascular Graft-Iliac Bifurcation in combination with the Atrium iCAST™ covered stent. Patients who do not meet the criteria will be excluded. A patient will be considered enrolled in the study once the delivery system of the study device has been inserted under the skin.

As depicted by Figure 1, all patients will be evaluated clinically and radiographically (when applicable) at pre-procedure, procedure, pre-discharge, 1, 6, 12, 24, 36, 48, and 60 months. Additionally, it is recommended that all previously enrolled patients who received the ConnectSX™ undergo CT follow-up to assess stent integrity every six months unless the stent has been relined to treat an observed or threatened Type III endoleak.

Patient with an aortoiliac or iliac aneurysm and an unsuitable distal sealing site for the Zenith® iliac leg component proximal to the common iliac bifurcation on the side of expected Zenith® Branch Endovascular Graft-Iliac Bifurcation implantation

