### **7.1. Risks and Foreseeable Adverse Device Effects**

Events known to be related to pre-existing conditions or existing at admission are not considered adverse events (e.g., prior medically-treated cardiac arrhythmia with no

change in status during the endovascular procedure). Additionally, common standard of care practices are not considered adverse events (e.g., centers located at high geographical altitudes that discharge all patients on home oxygen therapy regardless of procedure).

Adverse events that may occur and/or require intervention include, but are not limited to:

- Allergic or hypersensitivity reaction to stainless steel, polyester, polytetrafluoroethylene, gold, or nitinol
- Amputation
- Anesthetic complications and subsequent attendant problems (e.g., aspiration)
- Aneurysm enlargement
- Aneurysm rupture and death
- Arterial damage, including perforation, dissection, bleeding, rupture, and death
- Arterial or venous thrombosis and/or pseudoaneurysm
- Arteriovenous fistula
- Bleeding, hematoma, or coagulopathy
- Bowel complications (e.g., ileus, transient ischemia, infarction, necrosis)
- Cardiac complications and subsequent attendant problems (e.g., arrhythmia, myocardial infarction, congestive heart failure, hypotension, hypertension)
- Claudication (e.g., buttock, lower limb)
- Death
- Edema
- Embolization (micro and macro) with transient or permanent ischemia or infarction
- Endoleak
- Endoprostheses/stent: improper component placement, incomplete component deployment, component migration, suture break, occlusion, infection, stent fracture, graft material wear, dilatation, erosion, puncture, perigraft flow, and corrosion
- Fever and localized inflammation
- Genitourinary complications and subsequent attendant problems (e.g., ischemia, erosion, fistula, incontinence, hematuria, infection)
- Graft or native vessel occlusion
- Hepatic failure
- Impotence
- Infection of the aneurysm, device, or access site, including abscess formation, transient fever, and pain

- Lymphatic complications and subsequent attendant problems (e.g., lymph fistula)
- Neurologic or systemic complications and subsequent attendant problems (e.g., stroke, transient ischemic attack, paraplegia, paraparesis, paralysis)
- Pulmonary/respiratory complications and subsequent attendant problems (e.g., pneumonia, respiratory failure, prolonged intubation)
- Renal complications and subsequent attendant problems (e.g., contrast toxicity, insufficiency, failure)

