- Secondary intervention to treat a > 60% stenosis of the internal iliac artery (as identified through CT, angiography, or duplex ultrasound and confirmed by core laboratory) associated with clinical symptoms. Of note, this not only includes patients with internal iliac artery stenosis following successful placement of the Zenith® Branch Endovascular Graft-Iliac Bifurcation and covered bridging stent, but also any cases of technical failure resulting in occlusion of the internal iliac

artery during the initial implant procedure that require secondary intervention for associated clinical symptoms.

*Renal Failure:* Acute or progressive renal insufficiency leading to the need for dialysis or hemofiltration.

*Renal Insufficiency:* A rise in serum creatinine of more than 30% above the pre-procedure level, resulting in a serum creatinine level  $> 2.0$  mg/dl that does not spontaneously resolve (does not include those patients with a pre-procedure serum creatinine  $> 2.0$  mg/dl).

*Serious Adverse Event:* An adverse event that led to death, led to a serious deterioration in the health of the subject that resulted in a life-threatening illness or injury, resulted in a permanent impairment of a body structure or a body function, required in-patient hospitalization or prolongation of existing hospitalization, resulted in medical or surgical intervention to prevent permanent impairment to body structure or a body function, led to fetal distress, fetal death, a congenital abnormality or birth defect.

*Stent/attachment system fracture/break:* Fracture or breakage of any portion of the Zenith® Branch Endovascular Graft-Iliac Bifurcation or covered bridging stent or attachment system including metallic fracture or breakage of any suture material used to construct the stent or secure the stent or attachment system to the graft material as determined by the core laboratory and confirmed by CEC.

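### The adverse-event exemption for pre-existing conditions makes no exception for serious worsening, so under Section 13.0's heart-failure example such events can miss immediate submission and CEC attribution

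*Protocol*

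**What the plan says.** Section 7.1 exempts events known to stem from a pre-existing condition, and those "existing at admission are not considered adverse events (e.g., prior medically-treated cardiac arrhythmia with no" "change in status during the endovascular procedure" (the sentence is split by a page break). The list of possible adverse events that follows includes "Cardiac complications and subsequent attendant problems (e.g., arrhythmia, myocardial infarction, congestive heart failure, hypotension, hypertension" and "Anesthetic complications and subsequent attendant problems (e.g., aspiration".

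Section 13.0, which governs reporting, opens with the same clause on pre-existing conditions but continues differently: events "existing at enrollment are not considered adverse events (e.g., new treatment for congestive heart failure diagnosed prior to the procedure". For adverse device effects and serious adverse events it then says that "completed forms should be submitted to the data coordinating center immediately after the site learns of the event". It adds that the Data Safety Monitoring Board (DSMB) and the CEC review applicable adverse events.

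Attachment B opens its definition of a serious adverse event with "An adverse event that led to death, led to a serious deterioration in the health of the subject" and goes on to list hospitalization, or its prolongation, among the criteria. As shown, Attachment B has no entry for adverse event itself.

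Section 8.13 gives the CEC the task of judging whether an event was due to a pre-existing condition, the procedure, the technique or the device. Section 3.0 fixes the time of enrollment: "A patient will be considered enrolled in the study once the delivery system of the study device has been inserted under the skin".

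**The concern.** After an endovascular repair in patients with cardiac disease, a central safety question is whether later cardiac worsening comes from the old condition or from the procedure. Section 8.3 itself expects comorbidities that may confound the data, and the study has no control arm or blinding. Section 8.13 gives the question to an independent committee. The exemption makes the site answer it first, because an event that the site regards as known to come from the old condition is not an adverse event. Section 13.0's example points the site that way, since new treatment for known heart failure ordinarily means that something has changed. At stake are the timeliness of serious-event reporting and the independence of attribution. The endpoint analyses are not at stake.

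**Working it through.** No arithmetic applies, so the check sets the passages side by side and follows cases through them.

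| | Section 7.1 | Section 13.0 |
|---|---|---|
| Clause on known pre-existing conditions | present | present, same wording |
| Exception for serious worsening | none | none |
| Cut-off for existing events | admission | enrollment, meaning insertion of the delivery system |
| Example | treated arrhythmia, status unchanged during the procedure | new treatment for previously diagnosed heart failure |

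**Case 1: heart failure diagnosed beforehand, and a hospitalization for worsening with new treatment after the procedure.**
1. Under Section 13.0, if the site regards the event as known to be related to the old condition, it is not an adverse event. The section's example supports that reading.
2. Under Attachment B, a serious adverse event must first be an adverse event. Hospitalization cannot make an exempted event serious.
3. Immediate submission in Section 13.0 is tied to adverse device effects and serious adverse events. Unless the site sees a device effect, the duty is not triggered.
4. DSMB and CEC review in Section 13.0, and the monitoring described in Section 8.13, refer to adverse events. The CEC may therefore never receive the case.
5. Under Section 7.1 the result is not clearly different. The clause is the same, and the unchanged-status condition in its example concerns only the procedure. It is silent on later worsening.

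The main cause is thus the shared clause together with Section 13.0's example.

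**Case 2: an anesthetic complication that begins after admission and is present when the delivery system is inserted.** It did not exist at admission, so Section 7.1's cut-off does not exempt it, and the same section lists anesthetic complications as adverse events. It did exist at enrollment, so Section 13.0 exempts it on its words. Here the two sections conflict, but only for this interval.

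**Case 3: the 30-day morbidity endpoint.** The Attachment B index names its elements in their own terms, including congestive heart failure and arrhythmias that need new treatment, with no carve-out for pre-existing disease. The exemption is not written into the index.

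**The case against.** The strongest reply is that the two sections share one operative rule and that the examples only illustrate it. Section 7.1's example is limited to the procedure, so a reader might infer that Sections 7.1 and 13.0 contradict each other on post-procedure worsening. The text does not support that inference: Section 7.1 is silent there, and its general clause is as broad as Section 13.0's. This stands, and it moves the fault from a conflict between examples to the shared clause. It does not remove the fault.

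The word *known* also limits the exemption. Where the cause is unclear, the event is not exempt and should be submitted. That stands too, but it leaves the site to decide which cases are clear, and Section 13.0's example gives no warning about serious ones. Nor does that example mention hospitalization or serious deterioration, so its use in Case 1 is a permitted reading and not the only one.

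There are safeguards. Section 13.0's form covers adverse and other events, Section 8.8 puts intra-operative complications on the Event form, and Attachment A has the monitor review data sheets and records. A reader might infer that exempted events are lost altogether, which the protocol does not show. Some may be captured, and form instructions not shown here may help. But the monitor looks for adverse events, the very term whose reach is unclear, and later capture is not immediate submission.

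Finally, the cut-off difference has no bearing on heart failure diagnosed beforehand, which predates both cut-offs. It is a separate and narrow point.

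**Conclusion.** The concern holds as a defect in a stated reporting rule. Followed literally, Section 13.0 lets a serious worsening of a known condition bypass immediate submission and, possibly, independent attribution. The differing cut-offs are a second, smaller inconsistency. It should be corrected, but it does not threaten the trial's tests.

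The size cannot be given. The protocol states neither how many patients will have relevant pre-existing disease nor how often it will worsen. One patient in 40 is 1/40 = 2.5 percentage points of a patient-level rate, but that is the weight of one patient and not an estimate of anything missed. A reader might also infer that the 30-day morbidity result would be biased toward its 46% goal. The documents do not support that, because the index has its own element definitions and the protocol does not apply the exemption to them. No effect on the 6-month primary test is claimed either.

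The conclusion assumes that sites apply Section 13.0 as written and that no form instruction, which cannot be seen here, already overrides it.

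**What to change.** Reconcile Sections 7.1 and 13.0 with each other, with Section 8.13 and with the serious-event definition in Attachment B:

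1. Use one exemption sentence in both sections.
2. Use one cut-off in both. An admission cut-off would keep events arising between admission and insertion reportable, in line with Section 7.1's own list. The sponsor should choose and state it once.
3. Remove the heart-failure example from Section 13.0, or replace it with one that does not suggest that a changed condition is exempt.
4. State that post-procedure worsening of a pre-existing condition that meets an Attachment B seriousness criterion is submitted by the immediate route and attributed by the CEC. Non-serious progression may stay exempt if the single sentence says so consistently.

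Item 4 goes beyond harmonizing the wording, because neither section now contains such a statement. It is needed because harmonizing alone would leave the shared clause as it is. The morbidity index and the performance goals stay unchanged. The cost is short edits to two sections and the matching form instructions, somewhat more event forms and CEC cases, and possibly amendment approval under Section 11.0. If enrollment is under way, sites should check whether any serious worsening has already been left out of the immediate route.

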### **14.0. Ethical Considerations**

The investigator is responsible for obtaining approval of this clinical investigation plan by the relevant IRB. The Sponsor must be provided with a copy of this approval before delivery of any study devices. Furthermore, the investigator will ensure that local regulations concerning data protection are followed.

